Baseline Data Collection. La Frontera staff will obtain written informed consent in person from the first 150 eligible La Frontera participants, who will form the LinkUP study sample. Consent forms will be offered in both English and in Spanish by trained bilingual staff. The LinkUP consent form will include permission to share their de-identified data between the OnPoint SSP and our study team. LinkUP participants whose last La Frontera interview was more than 3 months ago will undergo a brief interviewer-administered survey that addresses their potential barriers to COVID-19 testing and vaccination (baseline LinkUP survey). Measures include beliefs and attitudes to COVID testing and vaccination as well as structural barriers (e.g., lack of transportation, homelessness); these measures are already approved by the IRB under the parent study (IRB #191390). Surveys will be conducted by La Frontera's interviewers using computer-assisted programmable interviewing (CAPI). Interviews are done under canopies outside La Frontera's mobile van with plexiglass partitions and PPE for both interviewer and participant, as we have done for the La Frontera parent study. Interviews will be offered in both Spanish and English by trained bilingual staff. Participants will also undergo venipuncture for SARS-Co-V-2 serology. Following centrifugation, sera are batched and delivered to Genalyte

(San Diego, CA), a CLIA-certified lab that has obtained Emergency Use Authorization for their SARS-CoV-2 Maverick® Multi-Antigen Serology Panel[20] and tests for IgM and IgG antibodies against 13 unique viral antigens. Sensitivity and specificity for detecting SARS-CoV-2 antibody is 96% and 98% respectively. Following the interview and blood draw, each of the 150 participants will be given a laminated coupon indicating the address of the closest OnPoint syringe exchange location and the program's schedule and encouraged to attend this location at their earliest convenience. All enrolled participants will be provided with \$20 to reimburse their time and the cost of transportation.

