Cluster Randomization. The four OnPoint syringe exchange locations will be randomized to deliver either the active (intervention) or didactic (control) version of the LinkUP intervention. The randomization scheme will be developed using an algorithm by La Frontera's statistician. Approximately three months into enrollment, there will be a one-week 'washout' period, after which time the two original intervention syringe exchange sites will become control sites and the two original control sites will become intervention sites. This cluster randomization scheme will help ensure that no neighborhood in San Diego County is denied access to the LinkUP intervention. By the end of the study, 75 LinkUP participants will have been randomized to an intervention site and 75 will have been randomized to a control site.

Participant Intake and Out-take Data at OnPoint Locations. OnPoint peer counselors will confirm that their client is a LinkUP participant when they are presented with the laminated card that was provided by LinkUP staff. They will then conduct a short 5 minute interview with the participant to obtain information on their COVID testing and vaccination history, their health status and any of their harm reduction needs to facilitate any referrals. After their visit, the peer counselor will supplement this with the Out-take data, which includes whether or not the participant received the LinkUP intervention and COVID-19 test(s). The information obtained will be shared through record linkage between OnPoint and La Frontera to confirm the study outcomes. Following the intake interview, the participant will either receive the LinkUP active or didactic intervention depending on the randomized allocation of the SSP site.

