Outcome Ascertainment: COVID-19 Testing & Vaccination. Outcome ascertainment will involve record linkage between La Frontera and OnPoint to determine which participants visited the SSP site they were referred to, and if they received the LinkUP intervention and COVID19 tests. Since LinkUP participants who refused COVID-19 tests at the SSPs and will have obtained COVID19 vaccination elsewhere, we will obtain these data in three ways: 1) *Self-report from La Frontera follow-up interviews* conducted 6 months after randomization. 2) *Record linkage with the CDPH's COVID-19 database* based on electronic health records (EHRs) for participants who provided a release of medical information. Record linkage will confirm if and where COVID testing was done elsewhere, if COVID-19 vaccine was administered, type, dates and # of doses, as well as hospitalizations and deaths. 3) *Biological validation* of vaccination will also be done based on COVID-19 serology conducted by Genalyte, which is being conducted as part of their follow-up visits in the parent study, La Frontera.

Analysis: Although the LinkUP trial is not powered to assess efficacy, we will conduct an intent-to-treat analysis following CONSORT guidelines[24] and register it at clinicaltrials.gov before enrolment. We will compare socio-demographics across the two study arms (intervention and control) to ensure balance, controlling for potential confounders and study location if there are significant differences. To obtain effect sizes and standard errors, percentages along with 95% CIs for those who a) had a COVID test within 6 months of the intervention and b) had \geq one COVID shot within 6 months of intervention, respectively, will be calculated for the two study arms. To obtain Risk Ratio estimates (intervention/control), we will use a logistic regression mixed model with a) had a COVID test; and b) had \geq 1 COVID shot within 6 months of intervention, respectively, as outcomes, considering intervention (active vs. didactic) as the primary fixed effect, potential covariates (e.g., age, gender, homelessness, income) and a random intercept for subject. We will also assess acceptability and feasibility of the LinkUP intervention among OnPoint investigators, staff, and clients through focus groups and CSAB meetings.

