The four OnPoint syringe exchange locations will be randomized to deliver either the active (intervention) or didactic (control) version of the LinkUP intervention. Approximately three months into enrollment, there will be a one-week 'washout' period, after which time the two original intervention syringe exchange sites will become control sites and the two original control sites will become intervention sites. This cluster randomization scheme will help ensure that no neighborhood in San Diego County is denied access to the LinkUP intervention. By the end of the study, 75 LinkUP participants will have been randomized to an intervention site and 75 will have been randomized to a control site.

OnPoint peer counselors will confirm that their client is a LinkUP participant when they are presented with the laminated card that was provided by LinkUP staff. They will then conduct a short 5 minute interview with the participant to obtain information on their COVID testing and vaccination history, their health status and any of their harm reduction needs to facilitate any referrals. After their visit, the peer counsellor will supplement this

with the Out-take data, which includes whether or not the participant received the LinkUP intervention, COVID-19 test(s). The information obtained will be shared through record linkage between OnPoint and La Frontera to confirm the study outcomes including COVID-19 vaccination. Following the intake interview, the participant will either receive the LinkUP active or didactic intervention depending on the randomized allocation of the SSP site. LinkUP participants will be compensated \$10 for their visit at OnPoint regardless of whether or not they choose to undergo a COVID test or receive a COVID vaccine.

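### Coupons have no time limit and all four sites swap after a one-week washout, so late attenders can receive the opposite version and dilute a contrast by referred arm; the arm-fixing date is implied, not stated

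*Combined protocol and SAP*

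**What the plan says.** Sites, not participants, are randomized. Section 9 (Cluster Randomization) says: "Approximately three months into enrollment, there will be a one-week" washout. Section 11 repeats the rule, "after which time the two original intervention syringe exchange sites will become control sites", and the two control sites change the other way. All four sites therefore swap.

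After the baseline interview and blood draw, each participant gets a laminated coupon with a site address and schedule and is "encouraged to attend this location at their earliest convenience" (Section 9, Baseline Data Collection; Section 11 says the same). No expiry date or visit window is given. After intake at the site, "the participant will either receive the LinkUP active or didactic intervention depending on the randomized allocation of the SSP site".

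On the analysis, "we will conduct an intent-to-treat analysis following CONSORT guidelines" (Section 9, Analysis). Section 9 (Outcome Ascertainment) uses record linkage to find "which participants visited the SSP site they were referred to". The follow-up interview is "conducted 6 months after randomization", while the testing outcome is whether a participant "had a COVID test within 6 months of the intervention". Section 5 says the results will supply effect sizes for a future efficacy trial.

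**The concern.** A one-week washout separates the two versions only if nearly everyone attends within about a week of getting the coupon. Nothing in the plan ensures this. Someone referred to an active site shortly before the swap, who comes after the washout, receives the didactic session. Someone referred to a control site in the same way receives the active one. This happens when the plan is followed exactly; it is not a protocol deviation.

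Under an intent-to-treat analysis by referred arm, both kinds of crossing pull the arms together. At stake is the effect size handed to the later trial. A confidence interval does not reveal a bias of this kind.

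The plan also leaves the arm-fixing date unwritten, so two analysts could classify the same late attender differently. The Out-take data record whether the participant received the LinkUP intervention, but Section 3 uses that name for both versions, so the field as described does not show which one was given.

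**Working it through.** **Which date fixes the arm.** The plan gives no figure to reproduce here, so the wording is compared first.

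- Pointing to referral: Section 9 speaks of participants randomized to a type of site, the Table 1 footnote of participants assigned to a site, and Outcome Ascertainment of the site of referral.
- Pointing to the visit: delivery depends on the site's allocation after intake, and the testing outcome is timed from the intervention.
- If referral: a late attender counts in one arm and receives the other arm's version.
- If visit: late attenders are classified correctly, but a participant who never attends has no clear arm. That does not fit the promised intent-to-treat analysis.

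Referral is the reading that fits the analysis, so the size is worked out on that basis.

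**Inputs from the documents.** Swap at about three months (taken as 13 weeks), washout of one week (weeks 13 to 14), 75 per arm, 150 in total.

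**Assumptions (not in the documents).** Uniform enrolment over weeks 0 to 13; a share f = 0.5 of the sample enrolled before the swap (75 people); none enrolled in the washout week; exponential time from coupon to visit with mean μ of 1, 2 or 4 weeks; everyone attends the referred site; the original version is kept through the washout.

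**Crossing share among pre-swap attenders.** A participant enrolled at week t crosses if the delay exceeds 14 − t. Averaging exp(−(14 − t)/μ) over t from 0 to 13 gives

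c = (μ/13) × exp(−1/μ) × (1 − exp(−13/μ)).

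- μ = 1: 0.0769 × 0.3679 × 1.000 = 0.028
- μ = 2: 0.1538 × 0.6065 × 0.998 = 0.093
- μ = 4: 0.3077 × 0.7788 × 0.961 = 0.230

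**Effect on the contrast.** Each crossing moves a person fully to the other version, in both directions, so the risk difference keeps a fraction 1 − 2fc, which is 1 − c at f = 0.5. The fraction does not depend on the attendance rate if that rate is the same before and after the swap. The last two columns assume rates of 30% and 50%, for a 20-point difference and a risk ratio of 0.50/0.30 = 1.67. The points lost are 20 × 2fc. The diluted ratio is (0.50 − 0.20fc)/(0.30 + 0.20fc).

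| Mean delay (weeks) | c | Of 75 | Risk difference kept | Points lost of 20 | Risk ratio |
|---|---|---|---|---|---|
| 1 | 0.028 | 2 | 97% | 0.6 | 1.64 |
| 2 | 0.093 | 7 | 91% | 1.9 | 1.59 |
| 4 | 0.230 | 17 | 77% | 4.6 | 1.48 |

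If 40% enrol before the swap, the risk difference keeps 98%, 93% and 82%. If 60% do, it keeps 97%, 89% and 72%.

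**Random error for comparison.** The 95% half-width of a risk difference, ignoring clustering, is 1.96 × √(2p(1 − p)/75): 12.8 points at p = 0.2 and 16.0 points at p = 0.5.

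**Effect of a three-week pause in coupons before the swap.** Enrolment then runs over weeks 0 to 10, and crossing still needs a visit after week 14:

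c = (μ/10) × exp(−4/μ) × (1 − exp(−10/μ)) = 0.002, 0.027 and 0.135.

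At f = 0.5 the contrast keeps 99.8%, 97% and 86%. If the swap stays at week 13 and the 75 × 3/13 = 17 deferred participants enrol after it, f = (75 − 17.3)/150 = 0.385. The contrast then keeps 99.9%, 98% and 90%.

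**The case against.** The size rests wholly on assumed delays, and parts of the plan favour prompt attendance: the coupon names the closest site (Section 9), transport costs are reimbursed, and the visit itself is paid. With a mean delay of one week the loss is 0.6 of 20 points, which is negligible. This is a pilot of acceptability and feasibility, expressly not powered for efficacy, and sampling error is larger than the bias at every delay considered. All of this stands. It does not show that delays are short: 68% of the parent study's participants are homeless (Section 7), and lack of transportation is among the barriers that the baseline survey measures.

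The dilution is also conditional. It arises only if the arm is fixed at referral. That stands too, and the point is worded accordingly.

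Three stronger readings are tempting, and the documents do not support them.

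- A reader might infer that washout-week visitors receive the opposite version or nothing. Sections 9 and 11 say that the sites change after the washout, so the original allocation holds during it.
- A reader might infer that the version received is lost. It can probably be reconstructed from site, visit date and swap date, and the described Out-take contents need not be a complete list. What is missing is an explicit requirement to record it.
- A reader might infer that the two six-month clocks are conflicting allocation rules. They are follow-up clocks. They leave the arm date open but do not set it, although a clock starting at the intervention has no start for someone who never attends.

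**Conclusion.** The concern holds in conditional form. With the arm fixed at referral, the plan as written lets pre-swap referrals receive the opposite version, and this biases the intent-to-treat risk difference towards no effect. With the arm fixed at the visit, non-attenders have no clear arm. Either way, the date has to be stated.

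The documents cannot give the size. In the illustration the contrast keeps between 97% and 77% of its true size for mean delays of one to four weeks. That does not invalidate the pilot, and the bias is smaller than its random error. It matters because it runs in one direction, enters a number intended for planning a later trial, and can be reduced at little cost. The change is worth making; confidence in the size is only moderate.

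**What to change.** 1. Define the intent-to-treat arm as the referred site's allocation on the coupon-issue date, for attenders and non-attenders alike. State that the original allocation holds for visits in the washout week.
2. Stop issuing coupons for a few weeks before the swap. Under the assumptions above, a three-week pause cuts crossing from about 3%, 9% and 23% of pre-swap attenders to about 0.2%, 3% and 14%.
3. Record the coupon date, visit date and version received in the Out-take data, so that crossing can be counted and a supportive analysis by version received can be reported.

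The cost is a few sentences of protocol text, three recorded items, and about 17 enrolments deferred by three weeks. Some crossing remains if delays are long. The calendar appears to allow the pause: two 13-week periods, the washout and the pause make 30 weeks from 1 March 2022, or late September 2022. Six months of follow-up then ends in late March 2023, before the RADxUP period closes on 31 August 2023 (Section 23). This again assumes 75 enrolments per 13 weeks.

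An option for the sponsor, outside the core fix, is to deliver the version in force on the coupon date even after the swap. That would remove crossing, but each site would deliver both versions for a time. Counselors told to avoid motivational interviewing with some participants would be using it with others, and such contamination can also bias towards no effect.

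### The 75/75 split is not assured by nearest-site coupons and a swap at about three months; swapping at the enrolment midpoint would give it, and site balance, in expectation

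*Combined protocol and SAP*

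**What the plan says.** Under Cluster Randomization in section 9, the randomized units are sites: "The four OnPoint syringe exchange locations will be randomized to deliver either the active (intervention) or didactic (control) version of the LinkUP intervention". The versions are exchanged once, at a time set by the calendar: "Approximately three months into enrollment, there will be a one-week 'washout' period", and then "the two original intervention syringe exchange sites will become control sites and the two original control sites will become intervention sites". The stated result is that "75 LinkUP participants will have been randomized to an intervention site and 75 will have been randomized to a control site"; section 11 repeats that "75 LinkUP participants will have been randomized to an intervention site", with 75 for control.

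Participants are taken in order of consent, "from the first 150 eligible La Frontera participants". Under Baseline Data Collection in section 9, each receives a coupon for the nearest OnPoint site. Section 11 says only that the coupon names one of the four sites and gives no rule. The version delivered depends on the site's allocation when the participant attends, and attendance has no deadline.

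The Analysis paragraph of section 9 plans a logistic mixed model with a random intercept for subject. Study location is adjusted for only when the arms differ significantly. The documents give no enrolment rate, enrolment length, expected numbers per site, site quota or arm cap, and no count that triggers the swap.

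**The concern.** The per-arm sizes are written as a product of the design, yet they depend on two quantities that the plan neither fixes nor forecasts: how many coupons are issued before the swap, and how participants divide between the two site pairs. The figure 75 is 150 divided by 2.

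More than the totals is at stake. The swap is useful because each site contributes to both arms. If it falls well away from the enrolment midpoint, most of the active arm comes from one pair of sites and most of the control arm from the other, so arm and neighbourhood overlap. If all 150 were enrolled before the swap, the trial would be a parallel comparison of two sites with two. Two neighbourhoods would then never be offered the active version, against the reason section 9 gives for swapping. The results are also meant to supply effect sizes for a later efficacy trial (section 5), so a site difference read as an arm effect would carry forward.

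**Working it through.** **Inputs from the documents.** N = 150; four sites, two per version in each period; one swap of all sites at about three months; stated result 75/75.

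**Inputs assumed, because the documents do not give them.** f = share of coupons issued before the swap (n1 = 150f). s = share of participants whose nearest site is in the pair that starts active, taken as stable over time.

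**The stated figure.** It cannot be derived from the procedure without f and s. As 150/2 it is reproduced.

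**Expected active count for a given allocation.**
150[fs + (1 - f)(1 - s)] = 75 + (2s - 1)(n1 - 75).
This equals 75 only if s = 0.5 or n1 = 75.

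| f | s | Calculation | Active/control |
|---|---|---|---|
| 0.25 | 0.7 | 150(0.175 + 0.225) | 60/90 |
| 0.6 | 0.6 | 150(0.36 + 0.16) | 78/72 |
| 0.7 | 0.7 | 150(0.49 + 0.09) | 87/63 |
| 0.8 | 0.7 | 150(0.56 + 0.06) | 93/57 |
| 1.0 (no second period) | 0.6 | 150(0.60) | 90/60 |

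**Site mix.** The first pair's share of the active arm is fs/[fs + (1 - f)(1 - s)]. Its share of the control arm is (1 - f)s/[(1 - f)s + f(1 - s)]. At f = 0.7 and s = 0.5 the expected totals are 75/75, but the shares are 0.35/0.50 = 70% and 0.15/0.50 = 30%. At f = 0.5 both shares reduce to s, so the expected site mix is equal in the two arms for any s.

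**Type I error.** Simulated null trials of 150, with equal site volumes and site effects of SD 0.5 or 0.8 on the logit scale (assumed):
- Unadjusted, f = 0.7: about 7-14% over both SDs. With 20,000 trials and a 30% outcome rate: 8.0% (SD 0.5) and 12.7% (SD 0.8).
- Unadjusted, f = 0.5: 4.8% and 4.6%.
- Unadjusted, f = 0.8: 13% and 22%. With no second period: 25% and 40%.
- Site as a fixed effect (1,500 trials, control rate about 40%): 4.5% and 5.0% at f = 0.7; 5.5% and 5.0% at f = 0.8.
- Site SD 0.2, unadjusted, f = 0.7: 5.1%.

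**What a swap at the 75th coupon achieves.** The expected split is 75/75 for every s. The realised count still varies, with SD = sqrt[150s(1 - s)]: 6.1 at s = 0.5 and 4.9 at s = 0.8. The 95% range for the active arm is 63-87 at s = 0.5 and 65-85 at s = 0.8. The chance of exactly 75/75 is 6.5-8.1%.

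**Period.** At f = 0.5 and s = 0.7, 0.35/0.50 = 70% of the active arm but 0.15/0.50 = 30% of the control arm enrol in period 1. A midpoint swap balances sites, not calendar time, so period must stay in the model.

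**Late attenders.** If 20 of the first 75 coupon holders attend after a swap at the 75th coupon, and arm is counted by version received, the effective n1 is 55. The expected active count is then 75 + (2s - 1)(-20): 71, 67 or 63 for s = 0.6, 0.7 or 0.8.

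**The case against.** A reader might infer that the procedure will miss 75/75, or that a count-based swap would guarantee it. The documents support neither. The starting allocation is random, so before it is drawn the expected split is 75/75 whatever the swap date. For a realised allocation it is also expected if the pairs have equal volume, or if enrolment runs at a steady rate for about six months, since three months is then the midpoint. The count-based swap works on average only, and 78/72 lies well inside the variation that remains after it.

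A reader might also infer that enrolment will be front-loaded. That is possible, because recruitment draws on a closed cohort contacted from one start date. But reaching 150 in about three months needs roughly 12 in-person consents a week (150/13 = 11.5). Slow enrolment fits the text equally well: a start on March 1, 2022, a study end on August 30, 2023 and six months of follow-up leave about 12 months for enrolment.

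The loss of precision is small. Relative efficiency, 4 × n_active × n_control/150², is 0.96 for 60/90 and 0.94 for 93/57, and the plan says the trial is not powered for efficacy. The inflated error belongs to an unadjusted comparison, and the between-site SD has no source in the documents.

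All of this stands, and it limits the claim. It does not remove it. The planned location adjustment depends on a significance test, and the planned random intercept is for subject, so the analysis as written does not reliably repair a lopsided swap. When there is no second period, site adjustment cannot help, because each site then supplies only one arm.

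**Conclusion.** The concern holds in limited form. The 75/75 split is not assured, and the plan gives no enrolment or site-volume assumption under which it would be expected for the realised allocation. Over the assumed values shown, the expected split ranges from 60/90 to 93/57. The effect of unequal totals on precision is at most about 6%. The larger matter is site imbalance from an off-centre swap, which can arise even when the totals are equal. It inflates unadjusted type I error to about 7-14% at f = 0.7 if sites differ by an SD of 0.5-0.8 logit, and hardly at all if they differ by 0.2. When a second period exists, always modelling site brings the error back to about 5%. The values of f, s and the site SD are assumptions, and the algebra takes the nearest-site rule in section 9 as the operative one. The change is worth making because it is cheap, and because it protects both the within-site comparison and the stated aim of reaching every neighbourhood.

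**What to change.** 1. Replace "Approximately three months into enrollment" as the trigger. Make the swap, with its one-week washout, at the enrolment midpoint: the 75th coupon if 150 remains the target, or half of the revised total if enrolment is projected to fall short.
2. In sections 9 and 11, restate 75/75 as the expected split, not a guaranteed one, assuming stable site shares.
3. Include site and period in the outcome models in all cases, in place of the significance-triggered adjustment for location.
4. Define the intention-to-treat arm by the site's status when the coupon was issued, so that coupons issued before the swap but used after it are handled consistently. Record the version actually received as well.
5. Reconcile the nearest-site referral in section 9 with the unspecified choice among four sites in section 11.

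The cost is protocol wording and a running coupon count, with no added participants. The one small drawback is that OnPoint will not know the exact swap date in advance.

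### Intent-to-treat is promised, but the six-month outcome window is counted from the intervention and the interview from randomization, with no participant-level start date and no rule for people who never attend OnPoint

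*Combined protocol and SAP*

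**What the plan says.** Under Analysis in section 9 of the combined protocol and SAP, the commitment is that "we will conduct an intent-to-treat analysis following CONSORT guidelines". The first outcome is to be summarised as "percentages along with 95% CIs for those who a) had a COVID test within 6 months of the intervention"; the second is at least "one COVID shot within 6 months of intervention". In the sentence on the risk-ratio model, the six-month phrase follows the vaccination outcome only, so it is unclear whether it also limits the testing outcome there.

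Under Outcome Ascertainment, the self-report interview is "conducted 6 months after randomization".

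Under Baseline Data Collection, participants consent at the van, receive a coupon for an OnPoint site and are "encouraged to attend this location at their earliest convenience". No deadline is set. The session is delivered at that later visit, after intake and before the test offer, and its receipt is recorded at out-take. Linkage with OnPoint is to "determine which participants visited the SSP site they were referred to" and whether they received the session and a test, so non-attendance is foreseen.

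Under Cluster Randomization, "The four OnPoint syringe exchange locations will be randomized to deliver either the active (intervention) or didactic (control) version". The sites swap arms about three months into enrollment. The same paragraph, repeated in section 11, says that 75 participants per arm will have been randomized to a site, but gives no date on which that happens for a person.

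**The concern.** Intent-to-treat needs a start date that every participant has, fixed before anything the arm could influence. Attending OnPoint and sitting through a session happen after assignment, and some people will never do either. A window that starts there has three consequences:

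- Non-attenders have no window, and the plan does not say how they are scored.
- A test or first dose obtained between coupon and visit falls outside the window.
- For someone who attends late, the window closes after the interview has taken place.

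The interview's own clock is no firmer at the level of the person, because sites are what is randomized and their allocation changes during enrollment. Someone referred before the swap who attends after it has no stated arm.

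The lay summary (section 5) says the results will be used to estimate effect sizes for a future efficacy trial. Those estimates are what this ambiguity affects.

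**Working it through.** The plan contains no power, attendance or uptake calculation to reproduce. Its only arithmetic here, 75 + 75 = 150, is consistent.

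**Step 1. The clocks side by side.**

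| Item | Counted from | Does every participant have this date? |
|---|---|---|
| Test and first-dose percentages | The intervention | Not if this means the session; non-attenders have none |
| Follow-up interview | Randomization | Not defined for a person |
| Coupon issue at the van | Not used as an anchor | Yes, all 150 |

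Outcome data for non-attenders do not depend on an OnPoint visit. The interview belongs to the parent study. Consent to release medical records is an inclusion criterion (section 10), and the state health department linkage relies on that release: "Record linkage will confirm if and where COVID testing was done elsewhere, if COVID-19 vaccine was administered, type, dates and # of doses". What is missing is the start date and the scoring rule, not a data source.

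**Step 2. How much of the window the interview covers.** For a visit *d* months after randomization, coverage = (6 − d)/6.

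- d = 1: 5/6 = 83%
- d = 2: 4/6 = 67%
- d = 3: 3/6 = 50%

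These figures concern self-report only. Vaccine dates come from the linkage and on-site tests from OnPoint, so the shortfall matters mainly for tests done elsewhere.

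**Step 3. Effect of the rule for non-attenders.** Illustration only; all inputs are assumed. Uptake among attenders is 50% active and 30% control, uptake among non-attenders is q = 10% in both arms, and no events occur before the visit. With attendance *a* in an arm:

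- All enrolled, real outcomes: rate = a × attender uptake + (1 − a) × q
- Attenders only: risk ratio = 0.50/0.30 = 1.67
- Non-attenders scored no: rate = a × attender uptake

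| Attendance, active / control | All enrolled | Attenders only | Scored no |
|---|---|---|---|
| 70% / 70% | 0.38/0.24 = 1.58 | 1.67 | 0.35/0.21 = 1.67 |
| 65% / 55% | 0.36/0.21 = 1.71 | 1.67 | 0.325/0.165 = 1.97 |
| 55% / 65% | 0.32/0.23 = 1.39 | 1.67 | 0.275/0.195 = 1.41 |
| 70% / 50% | 0.38/0.20 = 1.90 | 1.67 | 0.35/0.15 = 2.33 |
| 50% / 70% | 0.30/0.24 = 1.25 | 1.67 | 0.25/0.21 = 1.19 |

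With equal attendance of 40–80% and q of 5–20%, the all-enrolled ratio runs from 0.32/0.24 = 1.33 (a = 0.4, q = 0.20) to 0.41/0.25 = 1.64 (a = 0.8, q = 0.05). The other two rules give 1.67 throughout.

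**Step 4. Scale, ignoring clustering.** For 0.38 against 0.24 with 75 per arm, SE(log RR) = √(0.62/28.5 + 0.76/18) = 0.253, so 1.58 has a 95% CI of 0.96 to 2.60. At 60% attendance, the standard error of the between-arm attendance difference is √(2 × 0.6 × 0.4/75) = 0.08. A 10-point gap is therefore 1.25 standard errors, which is ordinary, and a 20-point gap is 2.5, which is large.

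**The case against.** The strongest reply is that *intervention* here means assignment. The Analysis paragraph does use the word as an arm label, in naming the two arms, the risk ratio and the fixed effect. This stands as far as it goes: the wording is ambiguous. But the window applies to both arms, the control session is itself called a version of the LinkUP intervention, and the out-take and linkage text treat the intervention as something a participant did or did not receive. The session is the more natural reading, and if assignment was meant the text should say so.

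Second, sections 9 and 11 describe participants as randomized or assigned to a site, and section 12 tells them of an equal chance of either component. A reader might infer that participants have no allocation at all. The documents do not support that: allocation to a site exists, and what is missing is its date.

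Third, a reader might infer that the plan will drop non-attenders or cannot count their outcomes. It says neither. An attenders-only analysis would contradict its own intent-to-treat commitment, and the outcome sources reach non-attenders. Still, intent-to-treat settles who is analysed and in which arm; it does not supply a start date. The nearest rule, in section 13, concerns refusal to join LinkUP, not non-attendance after joining.

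Fourth, this is a pilot declared not powered for efficacy, and Aim 2 speaks of acceptability and feasibility. That limits the consequence to the effect-size estimates.

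**Conclusion.** The point holds as a defect in the outcome definition. The stated anchor, on its natural reading, is a post-assignment event that some enrolled people will not have, and no section defines a participant-level date for either clock.

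The size is uncertain because attendance and uptake are not given. Under the assumed values, equal attendance gives 1.58 against 1.67, a shift that is small beside a confidence interval of 0.96 to 2.60. An ordinary 10-point attendance gap gives an all-enrolled ratio of 1.71 or 1.39, according to which arm attends more, against 1.67 among attenders. The larger departures need a 20-point gap. The illustration assumes no events before the visit, so it puts no figure on the events lost between coupon and visit.

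It would be too strong to say that any two analysts must reach different answers: with equal attendance, two of the three rules coincide. Nor do the documents show a bias in a known direction.

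**What to change.** In the Outcome Ascertainment and Analysis paragraphs of section 9:

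- Define time zero as the coupon-issue (referral) date for all 150.
- Define the intent-to-treat arm as the arm, on that date, of the site named on the coupon, whatever site is attended and whenever. State in advance which arm applies to a coupon issued in the washout week.
- Count tests and first doses within six months of that date, in both the percentages and the risk-ratio models.
- Keep non-attenders in the denominator, with outcomes from the interview and the state linkage. Do not drop them or score them as no by default.
- Obtain dates for tests done elsewhere from the existing interview or linkage request, since the plan lists dates only among the vaccine items.
- Leave the parent-study interview schedule as it is, record the actual interview date, and use the linkage where the interview falls short of the window. These documents do not show whether that schedule could be moved without cost.

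An attender-only analysis timed from the session can be kept as secondary.

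The cost is wording, a recorded date, site and arm at coupon issue, and a date for each off-site test. No new visit or data source is needed. The drawback is that the intent-to-treat effect is diluted by non-attendance and by attendance after the swap, and self-reported test dates carry recall error.
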